## 6 MILESTONES

**Table 6-1: Study Milestones**

Milestone	Treatment Group(s) a	Planned Date
Start of data collection b	Ipilimumab monotherapy	End of Q2 2019
Start of data collection b	Nivolumab monotherapy Nivolumab in combination with ipilimumab	End of Q1 2024
Progress report	Ipilimumab monotherapy	End of Q2 2022
Interim study report c	Nivolumab monotherapy Ipilimumab monotherapy Nivolumab in combination with ipilimumab	Q4 2026
End of data collection	Ipilimumab monotherapy	End of Q1 2029
Final report of study results	Ipilimumab monotherapy	End of Q3 2029
End of data collection	Nivolumab monotherapy Nivolumab in combination with ipilimumab	End of Q1 2033
Final report of study results	Nivolumab monotherapy Nivolumab in combination with ipilimumab	Q4 2033

a Study Milestones are planned as per nivolumab and ipilimumab commitments documented in nivolumab and ipilimumab EU RMPs.

b The start of data collection began in Q2 2019, when the Princess Maxima Center (PMC) officially confirmed its collaboration with the pediatric extension of the Dutch Melanoma Treatment Registry (DMTR) for patients treated with ipilimumab monotherapy. The start of data collection for patients treated with nivolumab monotherapy and nivolumab in combination with ipilimumab will be at the end of Q1 2024. However, because data will be collected retrospectively, all pediatric patients entered in the DMTR who received nivolumab monotherapy, ipilimumab monotherapy, or nivolumab in combination with ipilimumab will be included, even if the treatment started prior to the data collection start date.

c Interim study report is planned in Q4 2026 aligning with nivolumab EU RMP v30.1 and will include the nivolumab monotherapy, ipilimumab monotherapy and nivolumab with ipilimumab combination therapy cohorts in the interim analysis.

Abbreviations: Q, quarter.

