Long-term safety data in pediatric patients  $< 12$  years of age treated with nivolumab monotherapy, ipilimumab monotherapy, and nivolumab in combination with ipilimumab, will also be collected as a separate off-label use cohort, to increase study size given the rarity of the population of pediatric patients with melanoma. These data will be collected by the Dutch Melanoma Treatment Registry (DMTR), which consists of a consortium of organizations, including medical specialists, policymakers, healthcare researchers, patient advocates, and pharmaceutical companies. The DMTR was established in Jul-2013 at the request of the Ministry of Health to assure the safety and quality of melanoma care in the Netherlands through clinical auditing, health quality indicators, insight into real-world outcomes on effects and costs, and by serving as a platform for research. The DMTR is used to provide melanoma treatment centers with benchmarked feedback on the number of patients treated, treatment patterns, toxicity rates, and survival data. A large majority of patients receiving treatment for melanoma are expected to be enrolled in the DMTR, as participation in the registry guarantees reimbursement via the national health system for any approved melanoma therapy. Moreover, it is anticipated that data capture throughout patient follow-up will be complete, as data completeness and quality are monitored by the data managers within the web-based environment. In addition, patients are followed long-term in order to assess survival. The capture of Grade 3 and 4 immune-related AEs for adult patients (both treatment-

naive and previously-treated) receiving ipilimumab in clinical practice who were registered in the DMTR between Jul-2012 and Jul-2015 appeared to be complete and comprehensive.

With the extension of the indications for nivolumab and ipilimumab (as monotherapy or in combination therapy), as cited above, the DMTR will extend enrollment to this adolescent patient population (and patients younger than 12 years old, if available), thus collecting long-term data on the safety of nivolumab and ipilimumab to treat melanoma in pediatric patients.

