## **9.7 Data Analysis**

The data provided for pediatric patients will be divided into 2 cohorts, based on age at time of first dose of nivolumab monotherapy, ipilimumab monotherapy, or nivolumab in combination with ipilimumab treatment (index date). Cohort 1 will include patients 12 to under 18 years old at time of enrollment, and Cohort 2 will include patients < 12 years of age at the time of enrollment. Patients that were treated before the nivolumab or ipilimumab marketing approval date will be included and assigned to the appropriate age-based cohort, regardless of timing with respect to date of approval. Interim data on pediatric patients treated with nivolumab monotherapy, ipilimumab monotherapy, or nivolumab in combination with ipilimumab will be reported by BMS to the Pharmacovigilance Risk Assessment Committee in the Periodic Safety Update Report (PSUR), in the interim study report, and in the final study report.

A description of patient and tumor characteristics for all pediatric patients receiving alternative therapies will be provided, for the overall treatment landscape for this patient population.

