### **9.7.2 Secondary Objectives**

Descriptive statistics will be used to assess:

- Baseline characteristics, disease, and other clinical characteristics
- Treatment patterns, such as exposure to nivolumab monotherapy, ipilimumab monotherapy, or nivolumab in combination with ipilimumab (dose, frequency, treatment duration or number of infusions administered), and changes in nivolumab monotherapy, ipilimumab monotherapy, or nivolumab in combination with ipilimumab treatment following a Grade 3 to 4 AE, including

reasons for discontinuation of nivolumab or ipilimumab (including toxicity) and treatment with any subsequent therapies

- Observations related to parameters for growth and sexual maturation (height, weight, and Tanner stage)

Additionally, premature or delayed puberty will be analyzed based on gender and normal sexual maturation scales.

General descriptive statistics will include mean, median, minimum, maximum, and SD for continuous variables; count and percentages will be used to examine categorical variables.

Long-term outcomes for survival, time to progression, and PFS will be defined and analyzed as follows:

OS is defined as the time between the date of first treatment with study drug and the date of death. For subjects without documentation of death, OS will be censored on the last date the subject was known to be alive. OS medians and rates at several points of time (eg, at year 1 year, year 5), will be estimated using the Kaplan-Meier methodology for each treatment group.

Time to progression is defined as time from the first treatment with study drug to the date of the first documented progression, as assessed by investigator per the Response Evaluation Criteria in Solid Tumors (RECIST) v1.1.

The PFS is defined as the time between the date of the first treatment with study drug and the date of first documented tumor progression, based on investigator assessments (per RECIST v1.1), or death due to any cause, whichever occurs first. Subjects who die without a reported progression will be considered to have progressed on the date of their death. Subjects who did not progress or die will be censored on the date of their last (most recent) date of visit to the treating physician in the hospital.

Median PFS in each treatment group will be derived from the Kaplan Meier estimate.

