## **9.10 Other Aspects**

### **9.10.1 Strengths of Research Methods**

As discussed in [Section 7](#), a large majority of patients receiving treatment for melanoma in the Netherlands are expected to be enrolled in the DMTR, as participation in the registry guarantees reimbursement via the national health system for any approved melanoma therapy patients receive. Data capture throughout patient follow-up is expected to be complete, as data completeness and quality are monitored by the data managers within the web-based environment.

The capture of Grade 3 and 4 immune-related AEs for adult patients (both treatment-naïve and previously-treated) receiving ipilimumab in clinical practice who were registered in the DMTR between Jul-2012 and Jul-2015 appeared to be complete and comprehensive. In addition, patients are followed long term in order to assess long-term outcomes.

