## **10 PROTECTION OF HUMAN SUBJECTS**

### **10.1 Ethics Committee Review and Informed Consent**

This study does not require review and approval by ethics committees or informed consent. The DMTR will consent patients for their participation in the registry outside of the scope of this study.

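### OS and PFS are at risk of left-truncation bias: previously treated patients count from first dose if they are in the registry, and capture of those who died before registration is not assured

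*Protocol*

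**What the plan says.** **Who is included.** Table 6-1, footnote b, covers "all pediatric patients entered in the DMTR who received nivolumab monotherapy, ipilimumab monotherapy, or nivolumab in combination with ipilimumab" and says that they "will be included, even if the treatment started prior to the data collection start date". Section 9.7 adds: "Patients that were treated before the nivolumab or ipilimumab marketing approval date will be included and assigned to the appropriate age-based cohort". Inclusion therefore depends on being in the registry, not on when treatment began.

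**When the registry could enrol them.** The registry dates from July 2013 (section 7) and consisted of 14 adult centers (section 9.1). The pediatric center confirmed its collaboration in Q2 2019. Data collection for nivolumab and the combination starts at the end of Q1 2024 (Table 6-1). Section 10.1 states: "The DMTR will consent patients for their participation in the registry outside of the scope of this study".

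**Time origin and estimator.** Section 9.7.2: "OS is defined as the time between the date of first treatment with study drug and the date of death", and "The PFS is defined as the time between the date of the first treatment with study drug" and the first progression or death. OS medians and landmark rates and the PFS median come from Kaplan-Meier in each treatment group. No delayed entry is mentioned.

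**Completeness.** Section 9.10.1 expects most treated patients to be registered because "participation in the registry guarantees reimbursement via the national health system for any approved melanoma therapy". Section 7 says that data on children under 12 "will also be collected as a separate off-label use cohort".

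**What is not there.** Sections 9.3.1 to 9.3.3 list no registration date. Section 9.9 names small numbers and missing Tanner stage, but not selection. Annex 2 marks selection bias as not applicable (items 7.2 and 12.1.1).

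**The concern.** A child treated at the pediatric center before Q2 2019 could enter the registry through that center only after first dose. If such a child is more likely to be entered when still alive, the interval from first dose to registration contains no deaths by construction, yet ordinary Kaplan-Meier counts it as time at risk. Survival is then overstated, and more so in groups with more retrospective entrants.

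The protocol does not separate the two dates. Section 9.7 assigns cohorts by age at first dose and in the next sentence describes the same cohorts by age at enrollment. For a retrospective entrant these can differ by years.

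OS and PFS are secondary and descriptive, but they are named long-term outcomes of a safety study. The same mechanism touches the primary endpoint: death is one of the outcome categories for Grade 3-4 treatment-related events (section 9.3.1), so under-capture of early toxic deaths would lower the reported fatal toxicity.

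**Working it through.** The protocol gives no survival assumption or precision figure, so there is nothing of its own to reproduce. The question is how large the bias could be, and under what condition it vanishes.

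**Inputs from the protocol**
- Look-back from July 2013 to end of Q2 2019: W = 2019.5 − 2013.5 = 6.0 years. Collection to end of Q1 2029: F = 9.75 years.
- Look-back from July 2013 to end of Q1 2024: W = 2024.25 − 2013.5 = 10.75 years. Collection to end of Q1 2033: F = 9.0 years.

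**Assumptions, not in the protocol**
- Exponential survival with true 5-year OS of 30%, 50% or 70%.
- First doses uniform over W + F.
- All earlier patients registered at the collection start date.
- A proportion m of those already dead by then is missed.

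The 10.75-year case is an upper end, because a patient treated at the pediatric center between Q2 2019 and Q1 2024 could have been registered at treatment.

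**Result.** Kaplan-Meier 5-year OS, simulated with 20,000 patients per scenario:

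| W (years) | True | m = 0 | m = 0.5 | m = 1 | m = 1, delayed entry |
|---|---|---|---|---|---|
| 6.0 | 30% | 30.0% | 33.4% | 37.5% | 29.7% |
| 6.0 | 50% | 50.0% | 53.5% | 57.8% | 50.0% |
| 6.0 | 70% | 70.2% | 73.2% | 76.4% | 70.5% |
| 10.75 | 30% | 30.6% | 35.2% | 42.5% | 30.2% |
| 10.75 | 50% | 49.7% | 55.4% | 62.8% | 49.2% |
| 10.75 | 70% | 70.4% | 75.0% | 81.1% | 70.0% |

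The overstatement is nil at m = 0 apart from simulation error, 3.2 to 5.4 points at m = 0.5, and 6.4 to 12.8 points at m = 1. Delayed entry at registration recovers the true values.

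**Check in closed form with a different set of assumptions.** Take exponential OS with median 24 months (λ = ln 2/24). A fraction f of treated patients has registration delay D uniform on 0-48 months and is kept only if alive at D.
- P(T > D) = (1 − e^(−48λ))/(48λ) = 0.75/1.386 = 0.541.
- P(T > t and T > D) = (t/48)·e^(−λt) + (e^(−λt) − e^(−48λ))/(48λ). At 12 months this is 0.177 + 0.330 = 0.507; at 24 months, 0.250 + 0.180 = 0.430.
- Apparent OS(t) = [(1 − f)·S(t) + f·P(T > t and T > D)] / [(1 − f) + 0.541f].
- f = 0.5: (0.3536 + 0.2533)/0.7705 = 79% at 1 year and (0.25 + 0.2152)/0.7705 = 60% at 2 years, against true 71% and 50%.
- f = 0.3: (0.4950 + 0.1520)/0.8623 = 75% and (0.35 + 0.1291)/0.8623 = 56%.

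**Could the data reveal it?** Under complete capture, the share of earlier patients already dead at registration is 1 − (1 − e^(−λW))/(λW). With 5-year OS of 50% (λ = ln 2/5 = 0.1386) and W = 6, λW = 0.832 and the share is 1 − 0.565/0.832 = 32%. Among 10 late registrations, the chance that none was dead would be 0.679^10 = 2%. Registration date with vital status is therefore informative even at small numbers, though not conclusive: with 5 late registrations the chance is 0.679^5 = 14%.

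**The case against.** A reader might infer that OS and PFS do carry survivor bias. The protocol does not support that.

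- Footnote b speaks of treatment before data collection started, which is not the same as before registration. Some of these patients may have been registered when treated.
- Nothing requires a patient to be alive at entry. Section 10.1 says only that the registry obtains consent; it is silent on timing and on patients who have died.
- Section 9.4 points the other way: data are abstracted retrospectively from charts, which exist for deceased patients too; eCRF entry is stated for everyone treated at the pediatric center; and the registry is said to cover all Dutch patients with these diagnoses.

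This stands, and it makes the bias conditional. It does not settle the matter, because section 9.4 describes current practice and does not say that patients treated or deceased before the pediatric center joined are traced.

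A reader might also infer that no reimbursement incentive exists for off-label or pre-approval use. The protocol does not say how approval is judged. What it shows is narrower: the stated reason for completeness, as worded, does not reach those patients. A missing incentive would leave completeness unsupported; it would not prove that entry depends on survival.

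Sampling error is a fair point as well. With 10 patients, a 1-year OS of 71% has a standard error of √(0.71 × 0.29/10) = 14 points; with 30, 8 points. The bias may be smaller than the noise, but it runs in one direction and does not average out. Small numbers do argue against making delayed entry the main analysis.

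Finally, sensitivity analyses often belong in an SAP. Here, however, section 9.7.2 already fixes origin, censoring and estimator, and section 9.6 says that companies receive aggregate information from the registry. If the date is not requested, the sponsor may be unable to check later.

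**Conclusion.** The point holds as a risk, not as a demonstrated bias. The protocol admits previously treated patients on the condition of registry entry, starts their survival clock at first dose, and neither lists a registration date nor assures capture of those who died first. Its completeness argument does not, as worded, extend to the under-12 cohort or to pre-approval use.

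The size depends on an unknown, the share of pre-registration deaths that is missed. The overstatement of 5-year OS is zero with full capture, about 3-5 points if half are missed, and about 6-13 points if all are missed. These figures rest on exponential survival, uniform treatment starts back to July 2013 and registration at the collection start date, none of which the protocol states. The upper figures are close to a worst case. PFS shares the time origin and the direction of the risk, but its size was not computed.

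**What to change.** 1. **Section 9.3:** add the registry registration date and vital status at registration.
2. **Section 9.7:** report, by cohort and treatment, how many patients were registered after first dose and how many of those were already dead at registration.
3. **Section 9.7.2:** keep Kaplan-Meier from first dose. Add a sensitivity analysis of OS and PFS with delayed entry, each patient joining the risk set at the later of first dose and registration. State that it takes precedence if the data show that entry depended on survival.
4. **Sections 9.10.1 and 9.9:** limit the reimbursement-based completeness claim to approved use. List the selection risk as a limitation, including possible under-capture of early fatal toxicity.

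**Cost:** one extra date field with the vital status that goes with it, and an entry-time option in the survival program. The registry may already hold the date, but the protocol does not say so. The downside is an unstable early part of the delayed-entry curve: patients who died before registration contribute nothing to it, and with fewer than 10 patients a year one early death in a small risk set can pull the curve far down. That is why it should start as a sensitivity analysis.

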## 7 RATIONALE AND BACKGROUND

Clinical data regarding the effectiveness and safety of nivolumab (BMS-936558) monotherapy, ipilimumab (BMS-734016) monotherapy, or nivolumab in combination with ipilimumab for the treatment of pediatric patients with advanced (unresectable or metastatic) melanoma, or melanoma with involvement of lymph nodes or metastatic disease who have undergone complete resection are limited, due to the rarity of this patient population. Data on long-term outcomes, such as impact on growth and sexual maturation, for nivolumab and ipilimumab-treated pediatric melanoma patients are lacking.

Collection of long-term safety data in adolescent patients  $\geq 12$  years of age treated with nivolumab monotherapy, ipilimumab monotherapy, and nivolumab in combination with ipilimumab was agreed as a post-authorization safety study (PASS) with the European Medicines Agency during approval of the following variations for OPDIVO (nivolumab) and YERVOY (ipilimumab):

- EMEA/H/C/002213/II/0044 - Extension of indication for YERVOY to include the treatment of advanced (unresectable or metastatic) melanoma in adolescents 12 years of age and older
- EMEA/H/C/002213/II/0100 - Extension of indication for YERVOY to include in combination with nivolumab the treatment of adolescents 12 years of age and older, for advanced (unresectable or metastatic) melanoma
- EMEA/H/C/003985/II/0125/G - Extension of indications for OPDIVO to include adolescents aged 12 years and older in treatment of advanced (unresectable or metastatic) melanoma (nivolumab monotherapy), treatment of advanced (unresectable or metastatic) melanoma (nivolumab in combination with ipilimumab), and adjuvant treatment of melanoma with involvement of lymph nodes or metastatic disease who have undergone complete resection (nivolumab monotherapy)

Long-term safety data in pediatric patients  $< 12$  years of age treated with nivolumab monotherapy, ipilimumab monotherapy, and nivolumab in combination with ipilimumab, will also be collected as a separate off-label use cohort, to increase study size given the rarity of the population of pediatric patients with melanoma. These data will be collected by the Dutch Melanoma Treatment Registry (DMTR), which consists of a consortium of organizations, including medical specialists, policymakers, healthcare researchers, patient advocates, and pharmaceutical companies. The DMTR was established in Jul-2013 at the request of the Ministry of Health to assure the safety and quality of melanoma care in the Netherlands through clinical auditing, health quality indicators, insight into real-world outcomes on effects and costs, and by serving as a platform for research. The DMTR is used to provide melanoma treatment centers with benchmarked feedback on the number of patients treated, treatment patterns, toxicity rates, and survival data. A large majority of patients receiving treatment for melanoma are expected to be enrolled in the DMTR, as participation in the registry guarantees reimbursement via the national health system for any approved melanoma therapy. Moreover, it is anticipated that data capture throughout patient follow-up will be complete, as data completeness and quality are monitored by the data managers within the web-based environment. In addition, patients are followed long-term in order to assess survival. The capture of Grade 3 and 4 immune-related AEs for adult patients (both treatment-

naive and previously-treated) receiving ipilimumab in clinical practice who were registered in the DMTR between Jul-2012 and Jul-2015 appeared to be complete and comprehensive.

With the extension of the indications for nivolumab and ipilimumab (as monotherapy or in combination therapy), as cited above, the DMTR will extend enrollment to this adolescent patient population (and patients younger than 12 years old, if available), thus collecting long-term data on the safety of nivolumab and ipilimumab to treat melanoma in pediatric patients.

## **8 RESEARCH QUESTION AND OBJECTIVES**

### **8.1 Research Questions**

- What are the demographic and clinical characteristics of pediatric melanoma patients that receive treatment with nivolumab monotherapy, ipilimumab monotherapy, or nivolumab in combination with ipilimumab?
- What are the Grade 3 to 4 treatment-related AEs, including Grade 3 to 4 immune-related AEs in the endocrine system, reported in pediatric melanoma patients treated with nivolumab monotherapy, ipilimumab monotherapy, or nivolumab in combination with ipilimumab? How are Grade 3 to 4 treatment-related AEs reported in pediatric melanoma patients managed, and what are the outcomes? What events lead to discontinuation of study drugs?
- What are the long-term outcomes for pediatric melanoma patients treated with nivolumab monotherapy, ipilimumab monotherapy, or nivolumab in combination with ipilimumab (with emphasis on growth and sexual maturation)?

### **8.2 Objectives**

#### **8.2.1 Primary Objective**

The primary objective of this study is:

- To evaluate the Grade 3 and 4 treatment-related AEs, including Grade 3 and 4 immune-related AEs in the endocrine system, reported in pediatric melanoma patients receiving nivolumab monotherapy, ipilimumab monotherapy, or nivolumab in combination with ipilimumab, their management, and outcome

